5.5.2. Level of significance

A 5% significance threshold will be used.

5.5.3. Adjustments for covariates

No adjustment for covariates is planned for this study.

5.5.4. Handling of dropouts and missing data

Missing data will not be imputed, except dates (missing day) if needed in order to calculate durations.

5.5.5. Interim analyses

Two interim analyses are planned to gather early evidence on the performance and safety of the device. The interim reports will be integrated in the clinical data pool of the Sponsor for regulatory purposes.

- The first interim analysis will be performed when the first 10 patients have been included in the study and have undergone the planned robotic intervention with data recorded and validated in the eCRF, enabling the primary and secondary endpoints related to the intervention to be analyzed. All possible tables and listings will be produced (summarized in table below).
- The second interim analysis will be performed when all 25 patients expected have been included in the clinical investigation, with the identical conditions detailed in the previous point. All possible tables and listings will be produced (summarized in table below).

Objective	Endpoint	Population	Method	1 st interim	2 nd interim	Final
Feasibility	Technical success of the intervention	PP and ITT	Lesion	X	X	X
Performance	Needle placement accuracy	PP and ITT	Needle	X	X	X
	Number and grading of needle adjustments	PP and ITT	Needle, Lesion, Patient	X	X	X
	Immediate post intervention ablation success	PP and ITT	Lesion, Patient	X	X	X
	Long-term performance of ablation using the LTP rate	PP and ITT	Lesion			X
Safety	Number of AE recorded	SP		X	X	X
	Number of SAE recorded	SP		X	X	X
	Number of SADE recorded	SP		X	X	X

5.5.6. Multicentre studies

No comparison between the two sites is planned.

5.5.7. Multiple comparisons/multiplicity

No handling of multiple comparisons will be performed.

5.5.8. Examination of subgroups

No subgroup analyses are planned.

5.6. Patient data listings

Individual data listings will be provided in Word format. Patient data listings are listed in Section 13 of this SAP.

6. STUDY PATIENTS

6.1. Disposition of patients

The disposition of patients according to populations of analysis (Screened, ITT, PP, Safety) and visits (Visit 1 – Screening, Visit 2 – Intervention, Visit 3 – Follow up at 1 month, Visit 4 – Follow-up at 6 months and Visit 5 – Follow-up at 12 months, End of study) will be presented using frequency and percentages.

End of study information (normal end of follow-up (Visit 5 performed), AEs, screen failures, patient's will to withdraw from study, lost to follow-up, device deficiency or dysfunction, death and other) will be presented using frequency and percentages.

6.2. Protocol deviations

Validation of inclusion/exclusion criteria will be presented using frequency and percentages. All protocol deviations will be presented in patient data listings. Major deviations leading to exclusion from a population will be described as frequency and percentage of patients in the Screened population.

7. DEMOGRAPHIC AND BASELINE CHARACTERISTICS

Demographic and lung tumor characteristics will be presented on the ITT population using summary statistics for qualitative or quantitative parameters:

- Demographic data: age (years), gender, height (cm), weight (kg), Body Mass Index (kg/m²).
- Planned intervention: side of targeted lung (left, right or both [together/separately]), type of CT-Guided percutaneous treatment to be planned:
 - Ablation.
 - Biopsy.
 - Abscess drainage.
 - Fiducial marker insertion.
- Lung tumor type:
 - Primary tumor: NSCLC subtype, TNM stage (or other).
 - Metastatic tumor: primary cancer location.
 - Unidentified.
- Lung lesions:
 - Number of lesions intended to be treated per lung per patient.
 - Lesion details: lung side (left or right) and lobe (upper, lower or medium), lesion location (<10mm to mediastinum, <10mm to hilum, <10mm to pleura), tumor size (cm), estimated intra parenchymal distance (cm), intervention type performed (ablation, biopsy, abscess drainage, fiducial marker insertion).
- Planning with the Epione® device:
 - Number of needle trajectories
 - Needle identification information.

In addition, the following duration parameters will be presented only for the final analysis:

- Procedure time (post-intervention - pre-interventional CT-scan).
- Duration of Epione® device use (end of trajectory guidance – start of procedure planning).
- Duration of guidance (end of trajectory guidance - start of trajectory guidance).

Medical history, comorbidities, concomitant treatments (for the last 3 months) and planning with the Epione® device at inclusion will be described in patient data listings.

8. MEASUREMENT OF TREATMENT COMPLIANCE

Not applicable.

9. PERFORMANCE ANALYSES

Performance analyses will be conducted on the ITT and PP populations.

9.1. Primary endpoint

9.1.1. Definition of the primary variable

The primary endpoint is the technical success by lesion of each intervention.

Technical success by lesion is defined as:

When the needle(s) tip(s) reach(es) the target(s) with sufficient accuracy to pursue the intervention, and:

- Robotic needle insertion is performed without adjustment.
- Robotic insertion with only minor or medium adjustment(s).
- Robotic insertion is performed with one robotic major adjustment.

Technical failure by lesion is defined as:

When the needle tip does not reach the target with sufficient accuracy to pursue the intervention:

- If insertion of one or several needle(s) from the skin is fully manual.
- Failure of a robotic major adjustment.

The parameter of the primary endpoint consists of the percentage of robotically assisted lesion targeting and needle placements that were accurate enough to allow the percutaneous intervention.

The investigator will describe the technical success of the procedure for each lesion on a 2-point scale:

- "Is/are the needles positioned accurately enough to allow next step of the intervention?" = "Yes"
- "Is/are the needles positioned accurately enough to allow next step of the intervention?" = "No"

The performance endpoint is defined by "Is/are the needles positioned accurately enough to allow next step of the intervention?" = "Yes".

Note: if a lesion cannot be treated because of a major pneumothorax on the previous lesions treated, the lesion is excluded from the study and is not taken into account in feasibility statistics (negative answer to the question "Was the CT-Guided intervention maintained" with "pneumothorax" as reason specification).

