- **Visit 2** (treatment): the second visit consists of recovery of the signed informed consent form, confirmation of enrolment, validation of screening, and collection of demographic and tumor characteristics. Pre-intervention CT-guided image, planning of needle trajectory and insertion of needle into targeted area using study device, per-intervention CT-guided image and post-intervention CT-guided image will all be performed.
- **Visit 3:** Follow-up at 1 month (between 2 weeks and 6 weeks after treatment).
- **Visit 4:** Follow-up at 6 months (between 4 months and 8 months after treatment).
- **Visit 5:** Follow-up at 12 months (between 10 months and 14 months after treatment), end of study.

See Section 9 of the Clinical Investigation Plan for a detailed description of each visit.

Technical success is defined as:

When the needle(s) tip(s) reach(es) the target(s) with sufficient accuracy to pursue the intervention, and:

- Robotic needle insertion is performed without adjustment.

- Robotic insertion with only minor or medium adjustment(s).
- Robotic insertion is performed with one robotic major adjustment.

Technical failure is defined as:

When the needle tip does not reach the target with sufficient accuracy to pursue the intervention:

- If insertion of one or several needle(s) from the skin is fully manual.
- Failure of a robotic major adjustment.
- Note: if a lesion cannot be treated because of a major pneumothorax on the previous lesions treated, the lesion is excluded from the study and is not taken into account in feasibility statistics.

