4.2. Changes in the planned analyses

Any major/minor changes from the SAP will be discussed in the study report.

Definitions of the Per Protocol population and the Safety Population have been slightly modified from the definition in the protocol, indeed it has been clarified by the Sponsor that treated patients include all patients with an assistance of at least one needle placement with EPIONE®, even if the procedure (ablation, biopsy, fiducial placement or abscess drainage) was not performed using the EPIONE® device in accordance with protocol specifications.

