9.1.2. Statistical evaluation of the primary variable

Performance of the investigational device:

Frequency and percentage with “**Is/are the needles positioned accurately enough to allow next step of the intervention?**” = “**Yes**” reported by the investigator will be described by lesion. 95% CI of the percentage will be provided.

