9.2.2. Number and grading of needle adjustments

During or after each intervention, the number of needle adjustments will be reported, if necessary.

The number of needle adjustments to reach the target will be presented using qualitative and quantitative descriptive statistics:

- per needle.
- per lesion (sum per lesion).
- per patient (sum per patient).

Grading of adjustment(s) (minor, medium and major, refer to Section 3.5.2 for definitions) will be presented using frequency and percentage:

- per needle (at least one per needle).
- per lesion (at least one per lesion).
- per patient (at least one per patient).

In addition, quantitative descriptive statistics on the estimated corrective distance (mm) will be presented separately for each grading of adjustment (minor and medium):

- per needle (the highest per needle).
- per lesion (the highest per lesion).
- per patient (the highest per patient).

The highest distance was considered as the worst distance.

Finally, method of adjustment (using Epione® or other [CT guided, freehand]) will be presented in a listing.

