12. TABLES

The list of tables is provided below.

1. Patient disposition

- Table 1.1. Disposition of patients in populations of analysis – Screened population
- Table 1.2. Inclusion/exclusion criteria – Screened population
- Table 1.3. Protocol deviations – Screened population
- Table 1.4. Disposition of patients at study visits – Screened population
- Table 1.5. End of study information – Screened population

2. Demography and baseline characteristics

- Table 2.1. Demographic data – ITT population
- Table 2.2. Lung tumor characteristics – ITT population
- Table 2.3. Lung lesion details – ITT population
- Table 2.4. Planning with the Epione device – ITT population
- Table 2.5. Procedures duration – ITT population

3. Primary and secondary performance endpoints evaluation

- Table 3.1.1. Primary endpoint: Percentage of lesions with the needle(s) positioned accurately enough to allow the next step of the intervention – ITT Population
- Table 3.1.2. Primary endpoint: Percentage of lesions with the needle(s) positioned accurately enough to allow the next step of the intervention – PP Population
- Table 3.2.1. Needle placement accuracy measured during intervention (estimation) – ITT population
- Table 3.2.2. Needle placement accuracy measured during intervention (estimation) – PP population

Table 3.2.3. Needle placement accuracy measured after intervention (measure) – ITT population

Table 3.2.4. Needle placement accuracy measured after intervention (measure) – PP population

Table 3.3.1. Number and grading of needle adjustments – ITT population

Table 3.3.2. Number and grading of needle adjustments – PP population

Table 3.4.1. Immediate post-intervention ablation success (ablation only) – ITT population

Table 3.4.2. Immediate post-intervention ablation success (ablation only) – PP population

Table 3.5.1. Long-term performance of intervention using the Local Tumor Progression rate (ablation only) – ITT population

Table 3.5.2. Long-term performance of intervention using the Local Tumor Progression rate (ablation only) – PP population

4. Secondary safety endpoints evaluation

Table 4.1. Adverse Events (during the intervention) – Safety population

Table 4.2. Summary of Adverse Events – Safety population

Table 4.3. Adverse Events by System Organ Class and Preferred Term – Safety population

Table 4.4. Adverse Device Effects (ADEs) by System Organ Class and Preferred Term – Safety population

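### The primary analysis counts an accuracy-only Yes and never applies the SAP's own robotic conditions for technical success, so lesions outside the definition can count as successes

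*SAP*

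**What the plan says.** The protocol synopsis names technical success per lesion as the primary endpoint and does not define it further. The definition is in the SAP, in 3.2.1 and again in 9.1.1. The tip must reach the target accurately enough to go on, and one of three robotic conditions must also hold: no adjustment, only minor or medium adjustments, or "Robotic insertion is performed with one robotic major adjustment".

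Technical failure is introduced by "When the needle tip does not reach the target with sufficient accuracy to pursue the intervention". Two cases are listed under it: "If insertion of one or several needle(s) from the skin is fully manual", and failure of a robotic major adjustment.

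SAP 9.1.1 then gives the rule actually used: "The performance endpoint is defined by 'Is/are the needles positioned accurately enough to allow next step of the intervention?' = 'Yes". SAP 9.1.2 analyses the frequency and percentage of that answer, "reported by the investigator will be described by lesion. 95% CI of the percentage will be provided". Tables 3.1.1 (ITT) and 3.1.2 (PP) carry the matching title: "Percentage of lesions with the needle(s) positioned accurately enough to allow the next step of the intervention".

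On related data, SAP 4.2 explains that "treated patients include all patients with an assistance of at least one needle placement with" the device. SAP 9.2.2 tabulates the grade of adjustment "per lesion (at least one per lesion"), and gives the method of adjustment (Epione, CT guided or freehand) only in a listing.

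**The concern.** The definition has two parts and the analysis uses one. The study's question is whether the robot can place needles in the lung. An operator who abandons the robot and places the needle well by hand can truthfully answer Yes, because the question concerns final position only. That lesion then enters the numerator of the device's headline success rate.

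The error can run in one direction only: dropping a required condition can raise the rate but never lower it. The study is single-arm with no comparator, so this percentage carries the primary conclusion. It is produced at both interim analyses and at the end, and SAP 5.5.5 says the interim reports feed the sponsor's data pool for regulatory purposes.

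**Working it through.** **1. Definition against analysis rule.** The plan has no figure of its own to reproduce: SAP 3.4 sets 25 patients by an inclusion window, with no target rate, power or precision. The check is therefore a comparison of text.

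| Lesion, all with accurate final position | Meets the success definition (3.2.1, 9.1.1)? | Falls under failure, read literally? | Can be Yes in 9.1.2? |
|---|---|---|---|
| Robotic, no adjustment or only minor/medium | Yes | No | Yes |
| Robotic, one robotic major adjustment | Yes | No | Yes |
| One or more needles fully manual from the skin | No | No: the lead-in requires inaccuracy | Yes |
| Non-robotic major adjustment | No | No, same reason | Yes |
| More than one major adjustment | No | No, same reason | Yes |

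The last three rows are the problem. They lie outside the success definition, a literal reading of the failure definition does not catch them, and the analysis rule can count them as successes.

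**2. Do the analysis sets restore the condition?** No. Under SAP 4.2 and 5.3 a patient counts as treated if at least one needle placement was assisted, and PP keeps procedures not completed with the device. A lesion with one robotic and one manual needle can therefore sit in both ITT and PP with a Yes.

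**3. Do the secondary tables show the discordance?** Only in part. Grade is tabulated as at least one per lesion, so two major adjustments look the same as one. The number of adjustments is summed per lesion but not split by grade. The method appears only in a listing.

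**4. Possible size.** The documents give neither the number of affected lesions nor a lesion total (SAP 3.2.1 says at least 25 interventions). The counts below are assumptions: n lesions, all answered Yes, of which k miss the robotic conditions. The rate under the definition is x/n with x = n − k. The exact (Clopper-Pearson) 95% limits are:

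- lower = Beta quantile at 0.025 with parameters (x, n − x + 1)
- upper = Beta quantile at 0.975 with parameters (x + 1, n − x), or 1 when x = n

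| n | k | Rate under the definition | Exact 95% CI |
|---|---|---|---|
| 25 | 0 | 25/25 = 100% | 86.3 to 100 |
| 25 | 1 | 24/25 = 96.0% | 79.6 to 99.9 |
| 25 | 3 | 22/25 = 88.0% | 68.8 to 97.5 |
| 35 | 0 | 35/35 = 100% | 90.0 to 100 |
| 35 | 1 | 34/35 = 97.1% | 85.1 to 99.9 |
| 35 | 3 | 32/35 = 91.4% | 76.9 to 98.2 |

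The k = 0 rows are what the SAP's rule would report in every case. Each affected lesion is worth 1/25 = 4.0 points or 1/35 = 2.9 points. Three of them lower the lower limit by 86.3 − 68.8 = 17.5 points (25 lesions) or 90.0 − 76.9 = 13.1 points (35 lesions). Lesions are treated as independent; clustering within patients is ignored.

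**The case against.** The best defence is that the Yes/No item is simply how technical success is recorded. SAP 3.1, 3.5.1 and 9.1.1 present it that way, and the parameter text speaks of robotically assisted placements. SAP 3.2.1 also withdraws a patient when the whole intervention fails technically, so sites must judge failure on the day. Investigators may therefore answer No after a manual insertion. The case report form and the full investigation plan, which were not available for this review, may say so. This stands as a possibility. But the question asks about accuracy alone, no available text tells the investigator to answer No after a manual insertion, and 9.1.2 does not use robotic assistance as a filter.

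It can also be said that the failure bullets were meant to stand alone, so that manual insertion is a failure however accurate. That is probably the intent, since the manual-insertion bullet would otherwise add little. It strengthens the case for a fix: a lesion the sponsor regards as a failure can still be tabulated as a success.

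Keeping mixed robotic and manual lesions in the denominator is right, because removing them would flatter the device. The objection here is only to counting them in the numerator.

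Listings 3.1 and 3.3.1 to 3.3.4, with the listing of adjustment method, would let a reader find many discordant lesions by hand. That is true for a study of this size, but it does not correct the reported percentage, and needles manual from the outset might not appear in them. Finally, the study has no success threshold, so no formal decision can flip, and the counts above are hypothetical. Both points are accepted: what is at stake is the accuracy of the headline estimate.

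**Conclusion.** The concern holds, and the plan is wrong as written on this point. Followed literally, SAP 9.1.2 can report a success rate above the one its own definition in 3.2.1 and 9.1.1 would give, and the planned tables do not show by how much. The actual excess is unknown. If all 25 to 35 lesions are answered Yes, each lesion outside the definition overstates the rate by about 3 to 4 points, and three overstate the lower confidence limit by 13 to 18 points. If no such lesion occurs, or if investigators already apply the full definition when they answer, the two rates coincide. Confidence is medium because the form's completion instructions are unseen. The primary endpoint should be corrected before analysis.

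**What to change.** Derive the primary endpoint per lesion in SAP 9.1.1 and carry it into 9.1.2 and Tables 3.1.1 and 3.1.2:

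- **Success:** answer Yes, no needle inserted fully manually from the skin, and at most one major adjustment, which must be robotic.
- **Non-success:** every other attempted lesion, so that the two categories are exclusive and exhaustive. The pneumothorax exclusion stays as planned.
- State whether the limit of one major adjustment applies per needle or per lesion; the present text leaves this open.
- Show the raw Yes percentage as a supportive row, so that any difference is visible.

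The number, grade and method of adjustments are already collected. Needles inserted manually from the outset may not be: SAP section 3 defines an adjustment as a manipulation after the device-guided insertion, and no available text shows a field for them. Confirm that the form or source records identify them.

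The cost is SAP wording, one derived flag and possibly a source check. The reported rate may be slightly less favourable. If the Yes is already meant to carry the full definition, saying so in the SAP and checking it against the adjustment data costs even less.

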9.1.2. Statistical evaluation of the primary variable

Performance of the investigational device:

Frequency and percentage with “**Is/are the needles positioned accurately enough to allow next step of the intervention?**” = “**Yes**” reported by the investigator will be described by lesion. 95% CI of the percentage will be provided.

9.2. Secondary performance endpoints

9.2.1. Needle placement accuracy

The needle placement accuracy defines how accurately the operator has positioned the needle with respect to the planned needle trajectory.

On the control CT-scan (scan 3), the operator identifies the point he/she targeted on the planning, the presumed position is located by memory with the help of anatomical structures surrounding the area. Distance is estimated from the needle tip:

- 3D deviation (3D Distance from inserted needle point to planned needle point): estimation and measure.
- Lateral deviation (distance from orthogonal projection of planned needle point to needle axis): estimation and measure.
- Depth deviation (distance from orthogonal projection of planned needle point to inserted needle point on needle axis): estimation and measure.

In addition, the 3D distance from needle tip to lesion center (estimation) is also collected.

The assessment will be performed during (estimation) and after (measure) the intervention.

During the intervention:

- The operator will perform an evaluation of distances from target on the planning (planned needle tip position) to real needle tip on the final CT-scan performed after complete robotic needle(s) insertion and adjustment.
- The distances from planned needle tip position to tumor center will be compared to needle tip position to tumor center on the final CT-scan performed after complete robotic needle(s) insertion and adjustment.

After the intervention:

The same images will be reviewed and both the above will be measured using a ruler tool of the Epione® or equivalent, except for 3D distance to lesion center for which only the estimation per-operation is available (in case of multi-needle intervention, this estimation is not applicable and will not be presented).

Needle placement accuracy (mm) estimations and measures (seven parameters) will be described by needle as quantitative data.

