Primary objective and endpoint	Primary objective: Evaluation of the feasibility of the EPIONE device in assisting needles insertion in CT-guided intervention in the lungs. Primary endpoint: The primary feasibility endpoint is the technical success of the intervention per lesion.
Secondary objectives and endpoints	Secondary objectives: Evaluation of safety and performance parameters Secondary criteria: Safety 
Adverse Event(s) (AE): all AEs (serious and non-serious, including deficiency or dysfunction) and AEs related to the device or the intervention. Performance 
Assessment of the needle placement accuracy through an estimation of the distance from the needle inserted and the predefined planning;Assessment of the number and the grade of needle adjustments to achieve technical success;Assessment of post-intervention ablation success (ablation only);Assessment of local tumor progression.
Eligibility criteria	Inclusion criteria 
Patient ≥ 18 years,Patient for whom a percutaneous CT-guided intervention in lung has been prescribed and agreed by a multidisciplinary team of radiologists, surgeons and clinicians,Patient with a signed informed consent form.Patient covered by a social security system.

Investigation Number: QS-IS-G-H-2201

ClinicalTrials.gov ID: NCT05651867

CIV-ID: 2022-A01812-41

Document title: EGLE Clinical Investigation Synopsis

Doc No: CA-LU-SYN-020-(EN)

Revision: A

	
Exclusion criteria
 
• Patient unable to undergo general anesthesia,• Pregnant or nursing female, confirmed before the intervention• Patient already participating in another clinical study
Device and comparator	
The Epione investigational device is a user controlled, stereotactic accessory intended to assist in the planning and manual advancement of one or more instruments, as well as in verification of instrument position during Computed Tomography (CT) guided percutaneous procedures.
 
The Epione device is composed of 3 main components (Robot cart, Display cart with software and Navigation cart) and 3 instruments (Introducer guide, Patient reference and Navigation probe).
 
There is no comparator.

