3.5.2. Secondary Performance Variables

- Needle placement accuracy per needle after adjustment(s):**

Estimation of distance from target on the planning (planned needle tip position) to real needle tip on the control CT-scan (scan 3) performed after complete robotic needle(s) insertion and adjustment(s).

Estimation of distance from planned needle tip position to target tumor center compared to needle tip position to target tumor center on the final CT-scan performed after complete robotic needle(s) insertion and adjustment(s).

Estimated deviation distance: method

The operator will perform an estimation of the deviation between planned needle and the corresponding inserted needle on the control CT-scan (scan 3) performed after complete robotic needle(s) insertion and adjustment(s), to be representative of the

practice (the interventional radiologist only carries out the intervention when he/she considers the needle position being acceptable in regard with his/her objectives).

On the final CT-scan, the operator identifies the point he/she targeted on the planning, the presumed position is located by memory with the help of anatomical structures surrounding the area. Following collected distances are:

- 3D deviation (3D distance from inserted needle point to planned needle point): estimation and measure.
- Lateral deviation (distance from orthogonal projection of planned needle point to needle axis): estimation and measure.
- Depth deviation (distance from orthogonal projection of planned needle point to inserted needle point on needle axis): estimation and measure.

In addition, the 3D distance from needle tip to lesion center (estimation) is also collected.

- **The number of needle adjustments and grading to reach the target**

The adjustment can be:

- MINOR: Adjustment in depth, in the axis of the needle(s) (advance or retrieve).
- MEDIUM: Lateral adjustment, the needle does not leave the patient's body.
- MAJOR: Total removal of the needle(s) from the patient's body and reinsertion of the needle following the same planned trajectory, or a new trajectory to reach the target.

- **Post-intervention ablation success (ablation only)**

The per-intervention ablation assessment is performed between the pre-interventional and final post-interventional CT-scan (scan 4), in order to determine if the ablation is complete, incomplete or unclear, defined as the following:

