9.2.3. Immediate post-intervention ablation success (ablation only)

This secondary criterion determines if the ablation is complete, incomplete or unclear. In a complete ablation, the ablation volume completely covers the lesion, with sufficient MAM of 5 mm. Ablation assessment tool of EPIONE will be collected (complete ablation, incomplete ablation, unclear ablation) and summary statistics for qualitative parameters will be provided per lesion and per patient (the best result per patient).

9.2.4. Long-term performance of intervention using the Local Tumor Progression rate (ablation only)

Patients with tumor ablation will be evaluated for Local Tumor Progression (LTP) on follow-up CT imaging by the physician during the routine follow-up visits. This will be presented by lesion only.

Frequency and percentage of patients with any visible LTP on control imaging will be presented at approximately 6 months and 12 months. 95% CIs will be provided. The CT images of the ablation zone obtained at 1 month-FU routine visit will be considered as baseline imaging. The evaluation at later follow-up visits will be performed by comparing follow-up CT-scans to the baseline.

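### The SAP gives no method other than operator memory, aided by nearby anatomy, for locating the planned needle point, so six of the seven accuracy parameters rest on a recalled reference

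*SAP*

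**What the plan says.** SAP 3.5.2 and 9.2.1 describe how deviation is obtained. On the scan taken after robotic insertion and any adjustment, "the operator identifies the point he/she targeted on the planning, the presumed position is located by memory with the help of anatomical structures". In 3.5.2 the same rule runs directly into the list of distances: "the presumed position is located by memory with the help of anatomical structures surrounding the area. Following collected distances are".

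Under the rule in 9.2.1, the first entry reads "3D deviation (3D Distance from inserted needle point to planned needle point): estimation and measure". Two more entries, for the sideways error and the error along the needle, are likewise defined from the planned point and likewise marked for both versions.

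A further distance, from tip to lesion centre, is estimated only. Section 9.2.1 places the estimate during the procedure and the measure after it. For the measure it says: "The same images will be reviewed and both the above will be measured using a ruler tool of the Epione® or equivalent". That paragraph does not say how the planned point is found again, or by whom. No overlay of the plan and no independent reader is described.

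The accuracy scan is called the control scan (scan 3) in some sentences and the final scan in others, while 3.5.2 also uses final for scan 4.

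The protocol synopsis (Procedures to use the device) says the trajectory is planned in the device's software. SAP 3.3 says guidance follows that planning.

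**The concern.** A deviation has two ends. The inserted tip can be seen on the scan; the planned point cannot, and has to be placed. If it is placed from recall, error in the reference goes straight into the reported deviation, and measuring carefully between the two ends does not remove it. Because the needle is in view when the point is chosen, the recalled point could also be drawn toward it.

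Accuracy is part of the investigation's stated purpose in the synopsis. It is reported at both interim analyses and the final one, and the interim reports go into the sponsor's data pool for regulatory use (SAP 5.5.5). The SAP tabulates the estimate (Tables 3.2.1 and 3.2.2) and the measure (Tables 3.2.3 and 3.2.4) without saying which is the accuracy result. A reader may take agreement between them as validation.

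**Working it through.** **1. The plan's own count.** SAP 9.2.1 states seven accuracy parameters. Three deviations (3D, lateral, depth) × two versions (estimate, measure) + one estimated tip-to-lesion-centre distance = 3 × 2 + 1 = 7, which reproduces the figure. Each of the three deviations is defined from the planned point, so 3 × 2 = 6 of the 7 need it. The seventh does not.

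**2. Does the memory rule cover the measure?** The rule is explicit for the estimate. For the measure there are three supports: all three deviations listed under the rule are marked for both versions; the ruler step uses the same images; and no other rule for the planned point appears in either section. This is inference from the text, not a statement in it.

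**3. Illustrative size.** The documents give no deviation, recall error or pull, so every input here is an assumption:
- true 3D deviation d = 3 or 5 mm
- pull of the recalled point toward the tip p = 0, 25 or 50%
- random recall error with SD s = 0 or 2 mm per axis, equal in all directions

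Let m = (1 − p)d. With s = 0 the recorded mean is m. Otherwise it is s√(2/π)·exp(−m²/2s²) + (m + s²/m)·erf(m/(s√2)).

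For p = 0 and s = 2:
- d = 3: 0.518 + 4.333 × 0.8664 = 4.27 mm, and 4.27/3 = 1.42.
- d = 5: 0.070 + 5.800 × 0.9876 = 5.80 mm, and 5.80/5 = 1.16.

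| True d (mm) | Pull p | Recorded mean, s = 0 (mm) | Recorded mean, s = 2 mm (mm) |
|---|---|---|---|
| 3 | 0 | 3.00 | 4.27 (+42%) |
| 3 | 25% | 2.25 (−25%) | 3.83 (+28%) |
| 3 | 50% | 1.50 (−50%) | 3.48 (+16%) |
| 5 | 0 | 5.00 | 5.80 (+16%) |
| 5 | 25% | 3.75 (−25%) | 4.80 (−4%) |
| 5 | 50% | 2.50 (−50%) | 3.96 (−21%) |

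The range is −50% to +42%. When both mechanisms act they partly offset, giving 3.48 to 4.80 mm.

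**4. Does agreement between the versions validate the point?** A simulation of 300,000 draws let the true deviation vary between needles with mean 5 mm. It assumed 50% pull, recall SD 2 mm per axis, the same recalled point for both versions, and reading errors of 1 mm (estimate) and 0.5 mm (ruler). The mean difference between estimate and measure was about 0 and their correlation 0.83, yet the measure correlated only 0.35 with the true deviation. If the point were recalled afresh for the measure, less error would be shared, but agreement would still not test the point against the plan.

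**The case against.** The strongest reply is that the memory rule belongs to the estimate alone. In SAP 3.5.2 it sits under a heading about the estimated deviation. In 9.2.1 the next sentence speaks of estimating distance, and the paragraph on the later measure is silent on how the point is found. That wording is compatible with consulting the plan. This stands to the extent that a reader should not infer that the ruler measure has been shown to start from a recalled point. What remains is that the only method written down is memory, and the list under it names both versions.

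A reader might also infer that the plan is stored in the software and a better reference was ignored. The documents do not say that plans are archived or can be displayed on scan 3. The synopsis describes the device as assisting "as well as in verification of instrument position during Computed Tomography (CT) guided percutaneous procedures", but that is a general statement of use. The device description in section 6 of the Clinical Investigation Plan was not available for this review.

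A third tempting inference is that the figures flatter the device. Pull toward the needle is plausible but has no source in the documents, anatomical landmarks help the operator, and random recall error works the other way. With pull alone, the 25 to 50% shortfall simply restates the assumed pull.

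Finally, the endpoint is descriptive, and the two versions already have separate, labelled tables. That limits the consequence but does not supply the missing method.

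**Conclusion.** The point holds as a gap in method. Followed as written, SAP 3.5.2 and 9.2.1 rest six of the seven accuracy parameters on a planned point that the operator recalls with the aid of anatomy. This is explicit for the three estimates and a close reading for the three measures. The ruler does not correct that point, and agreement between estimate and measure would not validate it.

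The size and direction of any bias are unknown. The −50% to +42% range is an illustration on assumed inputs, not an estimate for this trial. The consequence is limited: this is a secondary endpoint with no threshold or test, and the primary yes/no technical success in SAP 9.1 does not use these distances. It is a low-cost improvement rather than a flaw that undermines the study.

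**What to change.** In SAP 3.5.2 and 9.2.1, keep memory-based location for the estimate only. For the measure:

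- Locate the planned tip and axis from the pre-intervention planning image and the Epione plan. View them beside scan 3, or displayed on it, where the plan is recoverable. Match by local landmarks where the lung has moved.
- Flag needles for which this is not possible as memory- or landmark-based, and report how many there are.
- State who measures, and use one name for the scan.
- Present the measure (Tables 3.2.3 and 3.2.4) as the accuracy result, label the estimate as supportive, and report the per-needle difference. Listing 3.2 is titled for values obtained during the procedure only, so the measured values should be listed too.

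No new scan or reader is needed: SAP 3.5.4 already collects images from before and during the procedure, and 3.5.2 already compares earlier and later scans to assess ablation. The cost is SAP wording and workstation time for the same operator. Needles already recorded may need re-measurement: the first patient was included on 30 November 2022, and the SAP relies on a CRF dated 31 March 2023, so collection began before the SAP was written. Alignment between plan and scan will carry its own error in a lung that has moved, which is why the flag is needed. If the plan was already consulted for the measure, one sentence saying so would answer the method question.
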